Leukotriene antagonists and 5-lipoxygenase inhibitors	Restricted	
Should not be used for more than 14 days. If treatment duration is expected to exceed 14 days the AstraZeneca study physician must be contacted.
 
If leukotriene antagonist is discontinued at Visit 1, approximately 72 hours have to elapse before performing spirometry testing at Visit 2.

Antibiotics	Restricted	Antibiotics to treat a COPD exacerbation should not be used for more than 14 days. If treatment duration is expected to exceed 14 days the AstraZeneca study physician must be contacted.

		Antibiotics taken for the prevention of a COPD exacerbation (e.g. macrolides, quinolones) are disallowed.
Omalizumab, denosumab or any other monoclonal or polyclonal antibody therapy (e.g. gamma globulin)	Prohibited	Disallowed if taken for any reason within 6 months prior to Visit 1 and during the study.
Allergen immunotherapy	Prohibited	Disallowed within 90 days prior to Visit 1 and during the study.
Live attenuated vaccines	Prohibited	Disallowed within 30 days prior to randomisation, during the treatment period and for 16 weeks (5 half lives) after the last dose of IP.
Ephedrine-containing medication	Prohibited	
Systemic treatment with potent Cytochrome P (CYP) 3A4 inhibitors (e.g., ketoconazole)	Prohibited	
Roflumilast (Daxas®, Daliresp®)	Prohibited	If Roflumilast is discontinued at Visit 1, approximately 7 days have to elapse before performing spirometry testing at Visit 2.

(a) COPD medication restrictions on the days of scheduled spirometry visits

Spirometry assessments will be performed at the study centre at scheduled visits (see [Table 2](#) and [Table 3](#)). There are restrictions regarding the subject’s COPD medications prior to the spirometry assessments.

Screening Visit 2: Subjects will be asked to withhold their usual double (ICS/LABA or LABA/LAMA) or triple (ICS/LABA/LAMA) medications on the morning of the screening pre and post BD spirometry (preferably should be at least 12 hours prior to the assessment/24 hours prior to the assessment for once daily medications) for the eligibility assessment (see section 3.1, inclusion criterion 3). In addition, SABA and SAMA should not be used within 6 hours of this spirometry assessment. The subject’s usual COPD medications may be administered following completion of the screening lung function procedures.

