4. STUDY PLAN AND PROCEDURES

Table 2 Study Plan – Enrolment, screening/run-in period

Assessment/Activity	Refer to section	Enrolment		Screening/run-in	
		V1 (w -4) ^a	V2 (w -3) ^a	V2 (w -3) ^a	V3 (w -1)
		Visit window (refer to section 4.1)		Day -7 (±3d)	
Informed consent	10.4	X			
Inclusion/exclusion criteria	3.1/3.2	X	X		X
Medical and COPD history	4.1.1	X ^b			
Concomitant medication	3.5.1	X	X		X
Adverse events	7.1	X	X		X
Acute exacerbation of COPD	5.1.1	X	X		X
Smoking status	4.1.1/5.2.2	X ^b	X		X
mMRC	5.1.3.3	X ^b			
CAT	5.1.3.4	X ^b			
Site assigns ePRO device and trains subject per the training guidelines	5.1.3		X		
Site to check ePRO compliance at each visit	5.1.3				X
Subject uses ePRO device daily at home to complete the following: 
 • Daily Morning – Nocturnal awakening 	5.1.3.5/5.1.3.6		X		X

Assessment/Activity	Refer to section	Enrolment		Screening/run-in	
		V1 (w -4) ^a	V2 (w -3) ^a	V2 (w -3) ^a	V3 (w -1)
		Visit window (refer to section 4.1)		Day -7 (±3d)	
		0-7 days prior to V2	Day -21 (±3 d)	Day -7 (±3d)	

 - Rescue medication - Major/minor symptoms • Daily Evening - EXACT-PRO/E-RS - Rescue medication Maintenance Medication					
Complete physical examination	5.2.1.1	X ^b			
Weight, Height	5.2.3	X ^b			
Vital Signs	5.2.4	X ^b			X
Supplemental oxygen (O ₂) status	5.3.7	X ^b			
Oxygen saturation (SpO ₂)	5.3.8	X ^b			
Chest x-ray (if applicable)	5.3.9	X ^b			
ECG	5.2.5	X ^b			X
Pre and Post BD spirometry	5.1.2			X	
Clinical chemistry	5.2.6	X			X
Haematology	5.2.6	X			X
Urinalysis	5.2.6	X			X
Serology (hepatitis B,C; HIV-1; HIV-2)	5.3.2	X			
Serum pregnancy test	5.2.7	X			
FSH ^c	5.2.7	X			

Assessment/Activity	Refer to section	Enrolment		Screening/run-in		
		V1 (w -4) ^a	V2 (w -3) ^a	V2 (w -3) ^a	V3 (w -1)	
		Visit window (refer to section 4.1)				
		0-7 days prior to V2	Day -21 (±3 d)	Day -7 (±3d)		
TB test (if applicable)	4.1.1	X ^b				
Pneumococcal and annual influenza vaccination, if applicable.	5.3.10	X ^d				

- ^a Visit 1 and Visit 2 can occur on the same day if there are no restrictions to medications for spirometry. Visit 2 may take place as soon as the medication restrictions prior to spirometry are met (see section 5.1.2), and should occur no later than one week after Visit 1.
- ^b These V1 procedures can be performed at any time between Visit 1 and Visit 2 inclusive.

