Subjects should avoid engaging in strenuous exertion for at least 30 minutes prior to spirometry measurements. Subjects should avoid eating a large meal for at least 2 hours prior to spirometry measurements at the centre. Forced expiratory manoeuvres should be performed with the subject seated in an upright position. If this is not comfortable for the subject,

standing is permitted. The same position should be used by the subject for each forced expiratory manoeuvre from enrolment throughout the study. The head must not be tilted during manoeuvres and the thorax should be able to move freely; hence tight clothing should be loosened. A nose-clip should be used for the manoeuvre. The subject from enrolment throughout the study should use mouthpieces of the same dimension and shape.

The forced expiratory manoeuvre (FEV₁ and FVC) should start with a maximal inspiration and then followed by a fast and forceful expiration that should last for at least 6 seconds. It is important to encourage the subject to continue the expiration to be fast and forceful throughout the manoeuvre. Ensure that none of the following has occurred: coughing during the first second, glottis closure, leak or obstruction of the mouthpiece (by the tongue).

Multiple forced expiratory efforts (at least 3 but no more than 8) will be performed for each centre spirometry session and the 2 best efforts that meet the ATS/ERS acceptability and reproducibility criteria will be recorded. The best efforts will be based on the highest FEV₁. The absolute measurement (for FEV₁ and FVC), and the percentage of predicted normal value (Quanjer et al 2012) will be recorded. The highest FVC will also be reported regardless of the effort in which it occurred (even if the effort did not result in the highest FEV₁).

Post-bronchodilator spirometry

Post-BD spirometry will be performed at V2 for all subjects (to evaluate inclusion criterion 3, see section 3.1).

Maximal bronchodilation will be induced using 4 inhalations of albuterol (90 µg metered dose) or salbutamol (100 µg metered dose) with or without a spacer device within 30 minutes ± 15 minutes of the final pre-BD spirometry measurement. Post-BD spirometry will be performed 20-30 minutes later. If a subject cannot tolerate 4 puffs of beta agonist, a lower number of inhalations may be considered at the investigator's clinical judgment.

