8.4.1.4 Forced expiratory volume in 1 second

The change from baseline to each of the post-randomisation visits (post Visit 4) up to and including the end of 56-week double-blind treatment visit (Visit 19) will be used as secondary efficacy variables. The pre-bronchodilator measurement recorded at Visit 4 will be used as baseline FEV₁. If the Visit 4 pre-bronchodilator measurement is missing, the last non-missing pre-bronchodilator value before Visit 4 will be used as baseline instead.

8.4.1.5 Annual rate of COPD exacerbations that are associated with an emergency room visit or a hospitalization

The annual rate of COPD exacerbations that are associated with an emergency room visit or a hospitalization will be a secondary efficacy variable.

In the statistical analysis, the number of COPD exacerbations that are associated with an emergency room visit or a hospitalization experienced by a subject during the 56-week double-blind treatment period will be used as response variable, and the logarithm of the subject's corresponding follow-up time will be used as an offset in the analysis to adjust for subjects having different exposure times during which the events occur.

Maximum follow-up time is approximately 56 weeks, and the follow-up time is derived as described in section [8.4.1.1](#).

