8.5.2 Secondary analysis methods

8.5.2.1 Analysis methods for secondary efficacy variables

Key secondary efficacy endpoints in this study are:

- Change from baseline in pre-dose/pre-bronchodilator FEV₁ at Week 56
- Change from baseline in SGRQ total score at Week 56

Other secondary efficacy endpoints include

- Proportion of subjects with ≥ 1 COPD exacerbation

- Time to the first COPD exacerbation
- Proportion of subjects with ≥ 4 -point decrease (improvement) in SGRQ total score at Week 56
- Annual rate of COPD exacerbations that are associated with an emergency room visit or a hospitalization
- Annual rate of hospitalizations, annual rate of hospitalizations and emergency room visits combined, annual rate of unscheduled outpatient visits including unscheduled visits to study centres and all unscheduled healthcare encounters due to COPD
- Rescue medication use (average puffs/day)
- Number of nights with awakening due to COPD and requiring rescue medication
- Change from baseline in E-RS total score and domain scores at Week 56
- Area under the curve (AUC) of E-RS total score
- BDI/TDI
- CAT
- EXACT-PRO

All the secondary efficacy endpoints will be analyzed in subjects with baseline blood eosinophil counts $\geq 220/\mu\text{L}$. In addition, the two key secondary endpoints will also be summarized in subjects with baseline blood eosinophil counts $< 220/\mu\text{L}$, $< 150/\mu\text{L}$, $150-219/\mu\text{L}$, $220-299/\mu\text{L}$, $300-449/\mu\text{L}$, and $\geq 450/\mu\text{L}$ separately for descriptive purpose only.

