Change from baseline in pre-dose/pre-bronchodilator FEV_1 at Week 56 will be compared between each of the three benralizumab dose groups and placebo using a repeated measures analysis on subjects with a baseline pre-dose/pre-bronchodilator FEV_1 and at least one post-randomisation pre-dose/pre-bronchodilator FEV_1 in the full analysis set. The dependent variable will be the change from baseline in pre-bronchodilator FEV_1 at post-baseline protocol-specified visits (up to the EOT visit). Treatment group will be fitted as the explanatory variable, and eosinophil cohort ($220-299/\mu\text{L}$ or $\geq 300/\mu\text{L}$), country, background therapy (ICS/LABA, LABA/LAMA, or ICS/LABA/LAMA), visit, the interaction between visit and treatment and baseline pre-bronchodilator FEV_1 will be fitted as covariates. Visit will be fitted as a categorical variable, and the variance-covariance matrix will be assumed to be unstructured. If the procedure does not converge then a compound symmetric variance-covariance matrix will be used instead. The model is:

*Change in FEV₁ = Treatment group + eosinophil cohort (220-299/ μ L or \geq 300/ μ L) + baseline FEV₁ + country + background therapy (ICS/LABA, LABA/LAMA, or ICS/LABA/LAMA) + visit + treatment*visit*

Change from baseline in SGRQ total score and three domain scores (symptoms, activity, and impacts) at Week 56 will be analyzed separately using a similar model as the above model for change from baseline in pre-dose/pre-bronchodilator FEV₁.

Proportion of subjects with \geq 4-point decrease (improvement) in SGRQ total score at Week 56 in each of the three benralizumab dose groups will be compared with the proportion in the placebo group using a Cochran–Mantel–Haenszel test controlling for eosinophil cohort (220-299/ μ L or \geq 300/ μ L), country, and background therapy (ICS/LABA, LABA/LAMA, or ICS/LABA/LAMA). Cumulative distribution function of absolute changes in SGRQ total score at week 56 will be plotted in a figure.

The proportion of subjects with \geq 1 COPD exacerbation during the 56 weeks of treatment will be addressed as a supportive variable to the primary objective. The proportion in each of the three benralizumab dose groups will be compared with the proportion in the placebo group using a logistic regression model with eosinophil cohort (220-299/ μ L or \geq 300/ μ L), country, background therapy (ICS/LABA, LABA/LAMA, or ICS/LABA/LAMA), and number of exacerbations in the year before the study as covariates.

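### Low-priority free gain: the Week 56 FEV1 model adjusts for Visit 4 FEV1 alone, although a pre-bronchodilator FEV1 is also scheduled for all subjects at Visit 2

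*Protocol*

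**What the plan says.** Protocol 8.4.1.4 defines baseline FEV1: "The pre-bronchodilator measurement recorded at Visit 4 will be used as baseline". If that value is missing, "the last non-missing pre-bronchodilator value before Visit 4 will be used as baseline instead".

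Section 8.5.2.1 names "Change from baseline in pre-dose/pre-bronchodilator FEV"1 at Week 56 as one of two key secondary endpoints. It prints the repeated-measures model in full. The terms are treatment group, eosinophil cohort, country and background therapy, together with "visit, the interaction between visit and treatment and baseline pre-bronchodilator" FEV1. There is one baseline FEV1 term and no term for an earlier visit.

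Table 2 (section 4) lists "Pre and Post BD spirometry" at Visit 2. Section 3.5.2(a) sets the medication rule for that session, "on the morning of the screening pre and post BD spirometry". Section 5.1.2 adds "Post-BD spirometry will be performed at V2 for all subjects (to evaluate inclusion criterion 3, see section 3.1"), and the bronchodilator is given within a set time "of the final pre-BD spirometry measurement". The last two extracts show that a pre-bronchodilator reading precedes the post-bronchodilator reading at Visit 2 for everyone.

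**The concern.** A single spirometry session measures a subject's underlying lung function with test error and day-to-day variation. A second session before randomisation usually carries information about Week 56 that the first does not. Here that second value is already collected for eligibility, and the protocol already accepts it as a stand-in baseline. When Visit 4 is present, which is the usual case, the printed model makes no use of it.

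What is at stake is precision on a key secondary endpoint whose significance thresholds can be strict. In Step 2 of section 8.5, Holm is applied to four tests (two endpoints by two doses) at 0.05, so the smallest p-value faces 0.05/4 = 0.0125. In Step 2a it is applied to two tests at 0.01, so the first threshold is 0.01/2 = 0.005. The protocol states no power for FEV1.

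**Working it through.** **The plan's own figures.** There is no FEV1 standard deviation, target difference, correlation or power to reproduce. The one stated sample size, 348 per arm for 90% power (8.2), concerns the exacerbation rate. A negative binomial Wald calculation with variance (1/(rate x exposure) + 0.4)/n per arm, rates 1.0 and 0.7 per 56 weeks, and both doses required at 0.04 gives 91.1% with no dropout and 89.8% with mean exposure 0.95. That agrees with the plan and does not bear on FEV1.

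**How comparable are the two sessions?**
- Interval: 3 weeks (±3 days) from Visit 2 to Visit 4, with COPD treatment unchanged (4.1.2).
- Withholding (3.5.2(a)): the same at Visit 2 and at Visits 4-19. Morning maintenance therapy is withheld, preferably for 12 h (24 h if once daily), and short-acting drugs for 6 h.
- Equipment and technique (5.1.2): the same.
- Time of day (5.1.2): the 6-11 AM recommendation covers both. The ±1.5 h match is tied to the randomisation session and binds later sessions only.

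**Formula.** Write a = corr(Visit 4, Week 56), b = corr(Visit 2, Week 56) and c = corr(Visit 2, Visit 4). With Visit 4 FEV1 as a covariate, change from Visit 4 and raw Week 56 FEV1 have the same residual variance, so on a unit scale:
- one baseline: 1 − a²
- two baselines: 1 − a² − (b − ac)²/(1 − c²)
- proportional fall: (b − ac)² / [(1 − c²)(1 − a²)]

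Example, a = 0.85, b = 0.84, c = 0.90: b − ac = 0.84 − 0.765 = 0.075. Then 0.075²/(1 − 0.81) = 0.0296, and 0.0296/0.2775 = 10.7%.

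**Assumed ranges (not in the document).** a 0.80-0.90; b equal to a or up to 0.03 lower; c 0.90-0.95. The first and last rows are the extremes of that grid.

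| a | b | c | One baseline | Two baselines | Fall | SE ratio |
|---|---|---|---|---|---|---|
| 0.80 | 0.77 | 0.95 | 0.3600 | 0.3590 | 0.3% | 0.999 |
| 0.85 | 0.83 | 0.95 | 0.2775 | 0.2723 | 1.9% | 0.991 |
| 0.90 | 0.88 | 0.95 | 0.1900 | 0.1836 | 3.4% | 0.983 |
| 0.85 | 0.82 | 0.90 | 0.2775 | 0.2616 | 5.7% | 0.971 |
| 0.85 | 0.84 | 0.93 | 0.2775 | 0.2594 | 6.5% | 0.967 |
| 0.85 | 0.84 | 0.90 | 0.2775 | 0.2479 | 10.7% | 0.945 |
| 0.90 | 0.90 | 0.90 | 0.1900 | 0.1474 | 22.4% | 0.881 |

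The gain vanishes when b = ac (for example b = 0.76 at a = 0.80, c = 0.95).

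**What the mid-range is worth.** For the planned 368 per arm, a 1.9% fall acts like 368/0.981 ≈ 375 and a 10.7% fall like 368/0.893 ≈ 412. Purely as an illustration, take a test with 70% power at two-sided 0.0125. Its power becomes Φ((2.498 + 0.524)/√(1 − fall) − 2.498): about 71% at a 1.9% fall, 72.7% at 5% and 75.4% at 10%. The 70% starting point is hypothetical.

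**The case against.** The strongest reply is that nothing is stated wrongly. The last pre-dose value at randomisation is a conventional and valid baseline, and an extra covariate is optional. That stands, and it sets the priority. What remains is that the protocol prints the full model, so the omission is a fixed choice and not a detail left to the SAP.

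The size is also uncertain, for three reasons that all stand:
- Every correlation is assumed. Within the assumed ranges the fall runs from almost nothing to about a fifth.
- The formula treats Week 56 as a single time point with raw correlations. The printed model is repeated-measures, already adjusts for country, background therapy and eosinophil cohort, and has no baseline-by-visit term. A single Visit 2 slope shared across visits need not be the best one for Week 56.
- Visit 2 is not a replicate of Visit 4. Table 1 allows roflumilast or a leukotriene antagonist to be stopped, or the ICS device to be switched, at Visit 1, shortly before Visit 2. The rescheduling instructions after early medication are written under Visits 4-19. Unacceptable Visit 2 sessions may be repeated (4.1.1), and eligibility is selected in that session. These features may pull the gain towards the low end, and they support keeping Visit 4 as the main baseline.

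A reader might infer that two interchangeable baselines exist and that one is thrown away. The documents do not support that: conditions are similar but not identical, the Visit 2 value is the fallback when Visit 4 is missing, and its presence for all subjects is by schedule.

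**Conclusion.** The point holds as a modest, low-priority efficiency gain. The FEV1 model leaves out a scheduled pre-randomisation measurement of the same variable. Including it would probably reduce Week 56 residual variance, by about 0.3% to 22% under the assumed correlations and about 2% to 11% in mid-range cases (standard error about 1% to 5.5% smaller). Because the value precedes randomisation, adding it cannot bias the treatment comparison.

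A reader might go further and infer that the planned analysis is invalid or that FEV1 power is materially short. Neither follows. The Visit 4 adjustment is valid, the protocol states no FEV1 power to fall short of, and the true correlations are unknown. The primary exacerbation endpoint, its sample size and its power are unaffected.

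**What to change.** In 8.5.2.1 (or by a sentence in the SAP), before unblinding, add Visit 2 pre-bronchodilator FEV1 as a second baseline covariate in the FEV1 repeated-measures model. Keep change from Visit 4 as the response and Visit 4 FEV1 as the first covariate, so the endpoint is unchanged. Enter Visit 2 as its own term and do not average it with Visit 4, since eligibility is selected at Visit 2. Optionally add its interaction with visit, so that the Week 56 slope is not forced to equal the slope at other visits. Where no acceptable Visit 2 value exists, enter the Visit 4 value.

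The cost is one degree of freedom. With the interaction it is one per post-baseline clinic visit: eight under the 4.2.1 schedule (weeks 4, 8, 16, 24, 32, 40, 48 and 56). Against about 1472 subjects at or above 220/µL, that is negligible. No new data are needed.

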5.1.3 Patient Reported Outcomes

Subjects will complete PRO assessments at the study center on paper and at home using a handheld electronic device (ePRO). PRO assessments must be collected in a systematic way to ensure data integrity. The following best practice guidelines should be followed when collecting PRO data at the site or via an ePRO device:

For PRO instruments administered during site visits

- Administer before other procedures
 - Always administer PRO instruments before other study procedures
- Provide the right environment
 - Provide a quiet and private location to complete the instrument
- No right or wrong answers
 - Remind subjects that there are no right or wrong answers and that we are asking them to complete these questionnaires because we're interested in hearing directly from them on how they feel.
- Help with procedural questions
 - Make sure the subject understands how to complete the instrument. Instrument instructions are usually self-explanatory but staff may answer questions about procedural issues like what it means to "tick a box".
- Avoid bias: do not clarify the meaning of questions or responses
 - Sometimes subjects will ask center staff to clarify the meaning of a question or response. To avoid introducing any bias, politely tell the subject that you cannot clarify items. Remind them that there are no right or wrong answers. Tell them that they should select the response that best answers the question as they understand it.
- No time limits

- Although most instruments require only a few minutes to complete the subject should be given as much time as is needed
- Review for completeness
 - Prompt review of the questionnaire for completeness will minimize missing data and data queries. If an item is left blank ask the subject if they intended to leave the item blank. Provide an opportunity for the subject to answer if they wish.
- Enter PRO data in appropriate modules of eCRF

For PRO instruments captured at home using an ePRO device

- Guidelines similar to paper
 - Many of the same principles apply for ePRO as paper. Remind subjects that there are no right or wrong answers, avoid bias by not clarifying items, remind subjects that they should complete the ePRO questions in a quiet and private location without help from others.
- Train the subject on ePRO device usage
 - Train the subject on how to use the ePRO device using the materials and training provided by the ePRO vendor
 - Provide guidance on whom the subject should call if they have problems
- Monitor compliance
 - Minimizing missing data is a key aspect of study success. Compliance must be checked at each study visit and should be checked more frequently to identify problems early. If compliance drops below 80% a check-in call from the site to ask the subject if they are having difficulties is highly recommended.
 - Recommended background medication compliance during the study is higher than 80%. It is recommended that compliance levels below 70% prompt the site/investigator to evaluate the reasons for low compliance and to provide re-education to the patient in regards to the importance of compliance. It is strongly recommended that when compliance level falls below 50% the site contacts the Study Physician in order to discuss the potential safety implications for the patient and future decisions.

Additional and more specific details concerning PRO instrument administration are provided in subsequent sections where each instrument is described.

